9. PHARMACOKINETICS

Blood samples for measurement of quizartinib and the active metabolite, AC886, plasma concentrations will be obtained from all subjects randomized to receive quizartinib on Day 1 and Day 15 of Cycle 1 before dosing and 1, 2, 4, 6, and 24 hours after dosing. The 24-hour samples must be collected before quizartinib dosing on Day 2 and Day 16. Samples will also be collected on Day 8 of Cycle 1 before dosing and 2 to 4 hours (taken immediately after ECG) after dosing. Thereafter, samples will be collected before dosing and 2 to 4 hours (taken immediately after ECG) after dosing on Day 1 of Cycles 2 and 3. At each time point, 2 mL of blood will be collected. Pre-dose samples should be taken within 0.5 hours before drug administration.

The 1, 2, 4, and 6 hour post dose samples should be taken within ± 0.5 hours of nominal time.

The 24 hour post dose samples should be taken within ± 3 hours of nominal time and before administration of the next dose.

Blood sampling, processing, storage and shipment instructions are provided in the lab manual.

10. PHARMACOGENOMICS AND PHARMACOPROTEOMICS

On Day 1, a buccal swab and whole blood samples (Pax gene DNA, Pax gene RNA, and PBMC) will be collected and shipped to a central laboratory. The PGX/PPX samples will be stored for up to 15 years, at which time they will be destroyed. PGX/PPX research may be conducted to explore PK and safety endpoints during this study or after the conclusion of this study. The results of the genetic and proteomic analysis will not be provided to subjects or the Investigator. Any information obtained from the PGX/PPX research will be the property of the Sponsor. Collection of these samples is not mandatory for participation in this study.

10.1. FLT3-ITD Mutation Assay

Of note, a companion diagnostic is being developed by Navigate for the US and European Union (EU) that will allow determination of FLT3-ITD mutation status from blood and/or bone marrow samples. The FLT3-ITD Mutation Assay is a polymerase chain reaction (PCR)-based molecular assay for detecting FLT3-ITD mutations utilizing genomic DNA isolated from blood or bone marrow. The ITD mutation always occurs in exons 14 and 15 of the FLT3 gene, which includes the juxtamembrane domain and the N-terminal part of the kinase domain. This region, when amplified by PCR using a single set of DNA primers that flank the region, yields ITD mutant reaction products that are greater in size than the 330-base pair non-mutant (ITD wild type) product. The FLT3-ITD Mutation Assay uses a fragment size analysis method to resolve and detect the different-sized PCR products by capillary electrophoresis.

11. PHARMACOECONOMICS

Resource allocation will be summarized and compared between study arms. The following variables will be measured to assess resource utilization in this study:

- Concomitant medications and procedures
- Hospitalizations
- Unscheduled clinic visits
- Emergency room visits
- Skilled nursing facility care
- Hospice care

12. DATA QUALITY ASSURANCE

This study will be organized, performed, and reported in compliance with the Sponsor's and the clinical research organization's (CRO's) standard operating procedures and working practice documents, and with ICH guidelines. Compliance will be achieved by study-specific monitoring of study sites, and by regular audits of the CRO's systems for handling, reporting, and archiving data.

The CRFs will be compared to source documents and reviewed at the study site for completeness by a clinical monitor. If necessary, the study site will be contacted for corrections and/or clarification. All data will be maintained in a study data base for analysis and reporting. Data captured electronically will be electronically transferred to the database. The database will receive a quality assurance check to ensure acceptable accuracy and completeness.

13. STATISTICAL METHODS PLANNED IN THE PROTOCOL AND DETERMINATION OF SAMPLE SIZE

13.1. General Considerations

This study is designed to compare the effect of quizartinib monotherapy and salvage chemotherapy on overall survival in subjects with FLT3-ITD(+) AML that is refractory or relapsed within 6 months after first-line therapy with or without consolidating HSCT.

13.2. Subject Disposition, Demographics, and Drug Administration

An accounting of all subjects randomized to the study will be reported. Demographics, disposition including reasons for withdrawal, administration of quizartinib and salvage chemotherapy, and major protocol violations will be tabulated and summarized with descriptive statistics for all randomized subjects. Major protocol violations will be identified in listings.

13.3. Sample Size Determination

Calculation of sample size is based on comparison of OS, the primary efficacy endpoint, in the 2 treatment groups (quizartinib and salvage chemotherapy) at a 2-sided significance level of 0.05, assuming that median survival is 3.9 months in the salvage chemotherapy group with an increase to 6 months, in the quizartinib group (hazard ratio 0.65). A total of 280 events (deaths) are necessary to meet a power requirement of 90%, given an interim analysis planned at 140 events (deaths) with O'Brien-Fleming boundary for superior efficacy and a conditional power (CP) of 10% for futility. For the purpose of sample size calculation, subjects are assumed to be accrued at a rate of 19.2 per month with a drop-out rate of 10%. The target accrual is a total of approximately 363 subjects randomized in a 2:1 ratio (242 subjects in the quizartinib group and 121 in the salvage chemotherapy group) over 17 months, to reach required number of events in a reasonable timeframe and to compensate for drop-outs. All calculations for sample size were performed using East® 6.3.

One formal interim analysis will be performed by an independent SAC and evaluated by an independent DMC according to statistical procedures defined a priori. At the interim analysis, the DMC may recommend 3 potential study options: (1) the study should be stopped due to futility; (2) the study should be stopped for superior efficacy in the quizartinib arm; or (3) the study should continue as planned to the total targeted number of 280 events.

It will be impossible to blind treatment allocations for individual subjects because of different treatment administration schedules and adverse events between the 2 study arms. However, the primary endpoint of survival is a robust endpoint and not susceptible to bias resulting from lack of blinding. Additionally, the Sponsor will not have access to aggregate efficacy data except when data from both treatment and control arms are combined. In addition, data relating to the primary endpoint of survival will be restricted so that the Sponsor will not have access to follow up data on individual subjects after 30 days of discontinuing study treatment. Approximately 80% of events will occur in this long term follow up period and so the Sponsor will be blinded to the primary endpoint of the study.

Randomization will be stratified by prior therapy and response, and pre-selected salvage chemotherapy:

Prior therapy and response:

- Relapsed in ≤ 6 months (not post HSCT)
- Refractory
- Relapsed in ≤ 6 months post allogeneic HSCT

Pre-selected chemotherapy, even for subjects subsequently randomized to quizartinib:

- High intensity chemotherapy (MEC; FLAG-IDA)
- Low intensity chemotherapy (LoDAC)

13.4. Primary Efficacy Analysis

Primary efficacy analysis will take place after the required number of events (deaths), 140 events (deaths) at the interim analysis or 280 events (deaths) at the final analysis, has occurred.

The primary efficacy endpoint (OS) analysis will be based on the stratified log-rank test. The stratification factors will be those used for randomization. A non-stratified log-rank test will be used as supportive evidence of efficacy. These analyses will be performed on the intent-to-treat (ITT) analysis data set, consisting of data from all subjects randomized.

Kaplan-Meier methods will be used to estimate OS in each treatment group, both overall and within subsets of subjects defined by the stratification factors. Estimates of median survival will be provided with 95% confidence intervals. Hazard ratio estimates will also be presented.

Overall survival will be censored at the last date when subjects were known to be alive. For primary analysis, overall survival will not be censored at the time of subsequent non protocol AML therapy, including transplantation.

Sensitivity analyses of OS will be performed by implementing an additional censoring rule: censoring at the date of HSCT for all subjects who have undergone HSCT. The sensitivity analyses will be described in detail in the statistical analysis plan. The primary efficacy analysis will be repeated for the per protocol set (PPS), which includes all subjects who are randomized and have no major protocol deviations.

Protocol deviations will be reviewed in a blinded fashion and categorized as major or minor before the interim analysis and data base lock and will be documented in a memo.

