3.3. Clinical Studies

A brief summary is given below. Refer to the current quizartinib [Investigator's Brochure](#) for additional information on clinical experience with quizartinib.

As of 22 Jan 2016, a total of 1289 subjects received quizartinib in 19 clinical studies including 624 subjects with either AML or solid tumors, 472 healthy volunteers, and 193 subjects with AML, ALL and MDS in 4 investigator sponsored trials.

Quizartinib was studied in 76 AML subjects in a Phase 1 study with intermittent dosing (14 days on drug followed by 14 days rest) from 12 mg to 450 mg, and continuous dosing at 200 mg and 300 mg.⁸ Plasma taken from subjects and assayed in an in vitro plasma inhibitory assay, showed maximal inhibition of FLT3-ITD signaling at 60 mg dose as early as 2 hours after the first dose. A marked reduction of FLT3-ITD phosphorylation in vivo was also observed at 60 mg and

higher doses. The overall response rate was 53% in FLT3-ITD(+) subjects and 14% in FLT3-ITD(-) subjects.

The response rate observed in Phase 1 was confirmed in the Phase 2, AC220-002 study of single agent quizartinib in relapsed or refractory AML. In this Phase 2 study a total of 333 subjects were enrolled in 2 cohorts; Cohort 1 included subjects 60 years or older who were relapsed or refractory to 1 line of therapy and Cohort 2 included subjects 18 years or older who were relapsed or refractory to salvage therapy or relapsed after HSCT. In Cohort 1, the CRc rate was 57% in FLT3-ITD(+) subjects with a median survival of 25.3 weeks.⁴ Cohort 2 showed a CRc rate of 46% in FLT3-ITD(+) subjects with a median survival of 24.0 weeks.⁵ Importantly, 35% of Cohort 2 FLT3-ITD(+) subjects were bridged to HSCT. Almost all (94%) subjects proceeding to HSCT had achieved a CRc or partial remission (PR) on quizartinib and their 1 year survival rate was 39%.

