5.2.5. Treatment with Quizartinib Following HSCT

Allogeneic transplant has become an accepted standard of care for consolidating newly diagnosed FLT3-ITD AML subjects in first remission.^{10,11,12} Additionally, treatment consensus guidelines recommend HSCT for subjects with relapsed AML regardless of FLT3-ITD status whenever feasible. Based on data from the Phase 2 studies, approximately 35% of subjects will likely be bridged to HSCT in the Phase 3 AC220-007 Study.

The post-HSCT relapse rate for FLT3-ITD positive AML subjects is higher than that observed for other AML sub-groups undergoing consolidation HSCT, and the leukemia cells at relapse are typically highly addicted to FLT3-ITD signaling.¹³

The use of a TKI to induce remission and then as maintenance post-HSCT has been established in BCR-ABL acute lymphocytic leukemia (Ph+-ALL). In adults with Ph+ ALL, HSCT is an established treatment standard of care,¹⁴ and BCR-ABL TKIs are not only used to bridge patients to transplant, they are routinely used post-HSCT to maintain remission and prolong survival.^{15,16} In terms of AML, a FLT3 inhibitor (sorafenib) currently approved for other oncology indications has been reported to have activity in the post-HSCT setting.¹⁷ Given current standard practice with BCR-ABL TKIs in Ph+ ALL, for subjects randomized to the quizartinib treatment group, quizartinib will be offered to those subjects undergoing HSCT with the aim of reducing the high risk of relapse post-HSCT and to evaluate whether administration of quizartinib before HSCT and as maintenance following HSCT, is of clinical benefit.

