13.10. Interim Analysis

The study design provides for one formal interim analysis when 50% (140) of the final number of events have been observed. At the discretion of the DMC, one of the following recommendations will be made at this interim analysis:

- Termination of the study for futility.
- Termination of the study for efficacy.
- Continuing the study as planned.

The DMC may only recommend that the Sponsor discontinue the study early only for either efficacy or futility.

The efficacy boundary will be based on the O'Brien-Fleming efficacy boundary derived from the Lan and DeMets error spending function, and the appropriate amount of α will be spent to ensure that the overall 1-sided type I error remains at 0.025. The futility boundary will be based on CP. At the time of the interim analysis, should the CP cross the futility boundary of 10%, the DMC will decide whether to recommend stopping the study. This decision will be based on the totality of information available at the interim analysis, including results of sensitivity analyses, secondary efficacy endpoint analyses, safety analyses, and benefit-risk analyses.

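### The one named OS sensitivity analysis censors at transplant as if transplant were unrelated to prognosis; label it descriptive and add a weighted analysis beside it (cheap improvement)

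*Combined protocol and SAP*

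**What the plan says.** Section 13.4 makes the primary OS analysis a stratified log-rank test on all randomized subjects, with no censoring at later therapy or transplant. It then adds one rule under the name of sensitivity analysis: "censoring at the date of HSCT for all subjects who have undergone HSCT". Detail is deferred to a statistical analysis plan, and the text available for review contains no further wording on the point. The non-stratified log-rank test and the per-protocol repeat, also in 13.4, do not deal with transplant.

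Four other places bear on this rule.

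- Section 3.3, on Cohort 2 of the Phase 2 study: "Almost all (94%) subjects proceeding to HSCT had achieved a CRc or partial remission (PR) on quizartinib". It puts one-year survival of these subjects at 39%.
- Section 5.2.5, on the present trial: "approximately 35% of subjects will likely be bridged to HSCT". The figure rests on Phase 2 quizartinib data and is not split by arm.
- Section 5.2.1 says that the Phase 2 transplantation rate exceeded that of a study of first salvage chemotherapy. It gives no figure.
- Section 5.6.4.5 lets subjects in the quizartinib arm resume quizartinib after transplant.

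Section 13.10 lists sensitivity analyses among the inputs that the DMC weighs if conditional power crosses the 10% futility boundary.

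**The concern.** Censoring at transplant is unbiased for survival without transplant only if, within each arm, transplant is independent of later survival. Here transplant selects responders. Once they are censored, the risk set that remains is richer in non-responders, so the arm's hazard rises. The rise is larger in the arm that loses the larger share of its surviving responders. If that is quizartinib, a real benefit looks smaller.

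At stake is interpretation. With no stated estimand or assumption, a reader may take a censored hazard ratio near 1 as evidence that the primary result depends on transplant, when part or all of the shift comes from the censoring rule. At the interim analysis the same figure could also be before the DMC in a futility discussion.

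**Working it through.** **1. The plan's own design figures.** Section 13.3 assumes "median survival is 3.9 months in the salvage chemotherapy group with an increase to 6 months, in the quizartinib group (hazard ratio 0.65", tests "at a 2-sided significance level of 0.05" and says "A total of 280 events (deaths) are necessary to meet a power requirement of 90" percent.

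- Medians: 3.9/6 = 0.65.
- Fixed design, 2:1 (Schoenfeld): (1.960 + 1.282)² / [(2/3)(1/3)(ln 0.65)²] = 255 deaths.
- Section 13.10 requires that "the overall 1-sided type I error remains at 0.025". Lan-DeMets O'Brien-Fleming bounds at 140 and 280 deaths are z = 2.963 and 1.969. Power at 280 deaths is then 92.4% without futility stopping.
- Section 13.3 adds "a conditional power (CP) of 10% for futility". Under the current trend this means stopping below z = √0.5 × (1.969 − 1.282 × √0.5) = 0.751, a hazard ratio above about 0.874. If that stop is always followed, power is 90.0%.
- Subjects: 19.2 × 17 = 326.4, and 326.4/0.90 = 363.

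The primary design reproduces. The point concerns only the sensitivity analysis.

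**2. Inputs for the check.**

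- From the documents: 2:1 allocation, 17 months of accrual, cut-off at 280 of 363 deaths, response on quizartinib of 47% (CRc) or 60% (CRc 47% + PR 13% at 30 mg).
- Assumed: response on chemotherapy 30%; median OS without transplant 9 months in responders and 3 in others; transplant only in responders, at 2 to 4 months; transplant cuts the hazard by 60%; transplant rates by arm as in the table.

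**3. Hand check of the mechanism.** Take response 47% vs 30% and transplant 28% vs 9%, with every transplant at month 3. Monthly hazards are ln2/9 = 0.077 in responders and ln2/3 = 0.231 in others. The shares alive at month 3 are 0.794 and 0.500.

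- Quizartinib: responders 0.47 × 0.794 = 0.373, others 0.53 × 0.5 = 0.265.
- Chemotherapy: responders 0.30 × 0.794 = 0.238, others 0.70 × 0.5 = 0.350.
- Hazards with nobody transplanted: (0.373 × 0.077 + 0.265 × 0.231)/0.638 = 0.141 and (0.238 × 0.077 + 0.350 × 0.231)/0.588 = 0.169. Ratio 0.84.
- After censoring, 0.373 − 0.28 = 0.093 and 0.238 − 0.09 = 0.148 responders remain. The hazards become (0.093 × 0.077 + 0.265 × 0.231)/0.358 = 0.191 and (0.148 × 0.077 + 0.350 × 0.231)/0.498 = 0.185. Ratio 1.03.

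Averaged with the unaffected months before transplant, the overall censored ratio falls between these two values, as the simulation shows.

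**4. Simulation.** Ranges show agreement between separate runs.

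| Response, Q vs C | Transplant, Q vs C | HR if nobody transplanted | HR censored at transplant |
|---|---|---|---|
| 47% vs 30% | 28% vs 9% | 0.83–0.84 | 0.93–0.94 |
| 47% vs 30% | 36% vs 20% | 0.84–0.85 | 0.93–0.94 |
| 60% vs 30% | 35% vs 10% | 0.74–0.75 | 0.81 |
| 47% vs 30% | 36% vs 12% | 0.84 | 1.00–1.03 |
| 60% vs 30% | 35% vs 20% | 0.74–0.75 | 0.73 |
| 47% vs 30% | 20% vs 20% | 0.84 | 0.78–0.79 |
| equal | equal | about 1.0 | about 1.0 |

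The fourth row is extreme. It needs 36/(47 × 0.794) = 96% of surviving quizartinib responders to be transplanted, and a 3:1 contrast in rates. The intention-to-treat hazard ratio in that row is 0.74 to 0.75.

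**5. A second model.** Keep exponential OS at the design medians (true hazard ratio 0.65) and vary the correlation between prognosis and transplant over 0, 0.5, 0.7 and 0.9.

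- Transplant 35% vs 10%: censored hazard ratio 0.65, 0.72, 0.77, 0.85.
- Transplant 35% vs 20%: 0.65, 0.68, 0.70, 0.73.
- Transplant 35% vs 35%: 0.61 to 0.65, so no attenuation.

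**6. Weighting at N = 363.** Stabilised inverse-probability-of-censoring weights by arm and response return 0.84 and 0.73 in the first and third table rows. The standard deviation of the log hazard ratio is 0.146 against 0.138 for simple censoring in one, and 0.144 against 0.150 in the other. In the extreme row it is 0.22 against 0.17.

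**The case against.** **The SAP may already deal with it.** Section 13.4 defers detail to the SAP, so a reader should not infer that no other analysis is planned. That stands. But the censoring rule itself is stated, and it needs an estimand and an assumption wherever the detail sits.

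**The size rests on assumptions.** This stands. A responder median of 9 months with the hazard cut by 60% implies exp(−12 × 0.4 × 0.077) = 69% alive one year after transplant, against the 39% in section 3.3. Suppose the 39% runs from transplant and the 60% cut is kept. The responder median without transplant is then ln2 × 0.4 × 12/(−ln 0.39) = 3.5 months, and the bias nearly vanishes (0.98 against 0.99–1.00). If the transplant benefit is dropped instead, 39% implies a median of ln2 × 12/(−ln 0.39) = 8.8 months, and the gap in the extreme case stays (0.84 against about 1.0). Also, 36% vs 12% at 2:1 averages (2 × 36 + 12)/3 = 28% overall, below the 35% of section 5.2.5.

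**The direction is not fixed.** This stands too, as the rows with 35% vs 20% and 20% vs 20% show.

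**A tempting stronger reading is that this analysis will turn a true benefit into no effect.** The documents do not support that. Selection alone gives about 1.0 only in the extreme row. A censored ratio of 1.00 also arises when the whole benefit runs through transplant or post-transplant quizartinib, with intention-to-treat ratios from 0.63 to 0.84. That is largely a change of estimand, and the analysis is then answering a different question.

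**Weighting may be unstable.** With about 0.12 × 121 = 15 control transplants, a many-covariate model fitted by arm would be fragile. In the extreme case unstabilised weights had a median maximum near 23. That argues for a small model with stabilised, truncated weights. It does not argue against weighting, since precision in the milder cases is about that of simple censoring.

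**Conclusion.** The concern holds as a cheap improvement. The rule in section 13.4 treats transplant as independent of prognosis, and sections 3.3, 5.2.1 and 5.2.5 make that implausible. If transplant is more frequent on quizartinib, the likely distortion is toward no effect: a no-transplant hazard ratio of 0.74 to 0.84 reads as 0.81 to 0.94, and about 1.0 only in an extreme case. With similar transplant rates the bias can be nil or can favour quizartinib.

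These sizes rest on assumed values for chemotherapy response, control transplant rate, timing of transplant, survival by response and the effect of transplant. The excess of transplants on quizartinib is inferred from a comparison across studies.

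Two further inferences should be resisted. The primary result is not weakened: it is not censored at transplant, and its alpha and 90% power are untouched. Nor does the analysis drive the interim decision: sensitivity results enter only once conditional power has crossed 10%, as one input among several.

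**What to change.** - Keep the simple analysis, state what it estimates and the independence it assumes, and label it descriptive.
- Add a stratified Cox analysis with stabilised, truncated inverse-probability-of-censoring weights. Use a small weight model: arm, time-updated response and at most a few baseline factors. Marrow assessments under MEC and FLAG-IDA are few, and long-term follow-up is by telephone every 3 months, so richer time-varying data will be thin.
- Report weight diagnostics: the range of the weights, the truncation point, and the share of responders transplanted in each arm.
- Report transplant rate and timing by arm.
- Give the DMC the simple and weighted results together.

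The cost is SAP wording and programming, with no new data and no change to the primary test. The weighted result relies on measured predictors of transplant, and it loses some precision if nearly all responders in an arm are transplanted.

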13.5. Secondary Efficacy Analysis

The secondary efficacy endpoint of EFS will be analyzed using the stratified log-rank test with covariates to control for response to first-line AML therapy and pre-selected salvage chemotherapy in the ITT. To maintain the overall type 1 error rate at the 0.05 significance level, hypothesis testing in the secondary analysis will be performed only if the null hypothesis in the primary analysis is rejected at the overall two-sided 0.05 significance level.

Analysis of the secondary efficacy endpoint will be repeated for the PPS.

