Primary efficacy analyses will take place after the required number of events (deaths), 140 events (deaths) at the interim analysis or 280 events (deaths) at the final analysis, has occurred.

The primary efficacy endpoint (OS) analysis will be based on the stratified log-rank test. The stratification factors will be those used for randomization. A non-stratified log-rank test will be used as supportive evidence of efficacy. These analyses will be performed on the intent-to-treat (ITT) analysis data set, consisting of data from all subjects randomized.

Kaplan-Meier methods will be used to estimate OS in each treatment group, both overall and within subsets of subjects defined by the stratification factors. Estimates of median survival will be provided with 95% confidence intervals. Hazard ratio estimates will also be presented.

Overall survival will be censored at the last date when subjects were known to be alive. For primary analysis, OS will not be censored at the time of receipt of subsequent non protocol AML therapy, including transplantation.

Secondary Efficacy Analysis

The secondary efficacy endpoint of EFS will be analyzed using the stratified log-rank test with covariates to control for prior therapy and response to first-line AML therapy and pre-selected salvage chemotherapy in the ITT population. To maintain the overall type 1 error rate at the 0.05 significance level, hypothesis testing in the secondary analysis will be performed only if the null hypothesis in the primary analysis is rejected at the overall two-sided 0.05 significance level.

These analyses will be repeated for the per protocol set (PPS). In addition, the primary efficacy endpoint (OS) and secondary efficacy endpoint (EFS) will be analyzed for pre-defined sub-groups.

Additional Efficacy Analyses

Statistical analyses of exploratory efficacy endpoints include:

- Kaplan-Meier analysis of duration of CRc and CR.
- Cochran-Mantel-Haenszel (CMH) test of CR rate
- CMH test of CRc rate
- CMH test of transplantation rate

Safety Analyses

The safety analysis set (SAF) includes all subjects receiving at least 1 dose of study treatment

(quizartinib or salvage chemotherapy).

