5. STUDY DESIGN

5.1. Overall Study Design and Plan

This is a Phase 3, randomized, open-label, 2-arm study to compare the effect of quizartinib monotherapy and salvage chemotherapy on OS in subjects with FLT3-ITD(+) AML that is refractory or relapsed within 6 months, after first-line therapy with or without consolidating HSCT. The control treatment is a limited choice of one of three standard chemotherapy regimens (low dose cytarabine [LoDAC]; mitoxantrone, etoposide, and intermediate-dose cytarabine [MEC]; or fludarabine, cytarabine, and granulocyte-colony stimulating factor (G-CSF) with idarubicin [FLAG-IDA]) which are widely used to treat patients with AML. Prior to randomization, the Investigator will pre-select one of the three salvage chemotherapy regimens for each subject; doses and the duration of study treatments are outlined in Section 5.6.4.2.

The study will utilize a group sequential design with 1 interim look at 0.5 information fraction (ie, 50% of planned number of events [deaths]). The target sample size will be approximately 363 subjects, randomized in a 2:1 ratio to receive quizartinib monotherapy (242 subjects) or salvage chemotherapy (121 subjects). One formal interim analysis will be performed by an independent statistical analysis center (SAC) and evaluated by an independent data monitoring committee (DMC), according to statistical procedures defined a priori. Based on the results of the interim analysis, the DMC may recommend that the study be terminated early for futility or for efficacy, or continue as planned. The tasks performed by the SAC and DMC are described in the DMC charter and Interim Analysis Plan.

If the study is positive at the pre-specified interim or final analysis, the sponsor may allow subjects who did not receive quizartinib to cross-over to the quizartinib monotherapy arm after database lock if the safety parameters in the eligibility criteria are met (see Section 5.4). The study will be unblinded after database lock.

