7.4. Event-Free Survival (EFS)

Event-free survival is the time from randomization until documented refractory disease, relapse after CRc, or death from any cause, whichever is observed first.

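### EFS has no stated bound at either OS look, which permits a small benefit-direction error excess; separately, one DMC sentence in 13.10 must be reconciled with 5.5

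*Combined protocol and SAP*

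**What the plan says.** **EFS.** Section 13.5 makes the EFS test conditional on OS and gives this as its means of error control: "To maintain the overall type 1 error rate at the 0.05 significance level, hypothesis testing in the secondary analysis will be performed only if" OS is rejected at the overall two-sided 0.05 level. The synopsis (Secondary Efficacy Analysis) says the same: "hypothesis testing in the secondary analysis will be performed only if the null hypothesis in the primary analysis is rejected".

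OS has two chances of rejection. Section 13.4 places the primary analysis when the required number, "140 events (deaths) at the interim analysis or 280 events (deaths) at the final analysis, has occurred". Section 5.1 foresees success at either: "If the study is positive at the pre-specified interim or final analysis". Section 13.10 describes Lan-DeMets O'Brien-Fleming spending for the OS boundary, so that the "overall 1-sided type I error remains at 0.025". It also lists secondary endpoint analyses among the interim results, so EFS results will exist at 140 deaths.

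The supplied text gives no EFS level, boundary or spending function at either look. It does not say whether EFS may be retested if OS is rejected at the interim and EFS is not. Section 7.4 makes death an EFS event: "Event-free survival is the time from randomization until documented refractory disease, relapse after CRc, or death from any cause".

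**DMC.** The synopsis and sections 5.1 and 13.3 list futility, efficacy or continuation as the interim options. Only section 13.10 adds a limit: "The DMC may only recommend that the Sponsor discontinue the study early only for either efficacy or futility". Section 5.5 names unacceptable risk to subjects among the conditions that may warrant termination.

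**The concern.** Testing EFS only after OS protects EFS fully when there is one analysis. With two looks, the OS result also decides which look supplies the EFS test. Deaths count in both endpoints, so the two statistics are positively correlated. When OS crosses its high interim bound, the EFS statistic at that look tends to be high by chance too. A fixed EFS critical value of 1.96 makes no allowance for this.

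EFS is the one endpoint tested under error control after OS. Without a bound per look, a claim of EFS benefit could carry somewhat more than a 0.025 risk of error in that direction. A level chosen once the data are known would also weaken the claim, especially after an early OS stop.

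On the DMC sentence, what is at stake is clarity: taken literally, it leaves no safety-based recommendation at the formal look.

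**Working it through.** **1. The plan's OS design.** Inputs from 13.3 and 13.10: hazard ratio (HR) 0.65, 2:1 allocation, two-sided 0.05, 90% power, looks at 140 and 280 deaths, 10% conditional power for futility.

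- Fixed design: (1.960 + 1.282)² / [(2/9) × (ln 0.65)²] = 10.507 / (0.2222 × 0.1856) = 255 deaths.
- Two looks, with futility treated as binding at interim z < 0.751 (10% conditional power under the current trend): 280 deaths give 90.0% power. The plan's figure reproduces.
- Spending at information 0.5: 2[1 − Φ(2.241/√0.5)] = 0.00153 one-sided. The OS bounds are z = 2.963 and 1.969, for an overall one-sided 0.025.
- OS drift at HR 0.65: 0.4308 × √(280 × 2/9) = 3.398. At the interim, 3.398 × √0.5 = 2.403, so OS crosses there with probability 1 − Φ(2.963 − 2.403) = 0.288.

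**2. EFS error under the stated order.** Let O1, O2 be the OS statistics and E1, E2 the EFS statistics at the two looks. Assume no EFS effect and one EFS test at z = 1.96, at the look where OS crosses (the plan gives no level):

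error = P(O1 > 2.963, E1 > 1.96) + P(O1 ≤ 2.963, O2 > 1.969, E2 > 1.96).

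One-sided error by normal simulation (2 to 3 million draws), with 50% EFS information at the interim (assumed):

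| OS-EFS correlation (assumed) | OS HR 0.65 | HR 0.75 | HR 0.80 |
|---|---|---|---|
| 0.25 | 0.026 | 0.022 | 0.017 |
| 0.3 | 0.027 | 0.023 | 0.018 |
| 0.5 | 0.029 | 0.027 | 0.024 |
| 0.7 | 0.029 | 0.031 | 0.029 |

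The maximum for correlations 0.3 to 0.7 over OS HR 0.60 to 1.00 is 0.031. If OS has no effect, the error is 0.002 to 0.009. Two-sided totals at HR 0.65 are 0.045, 0.043 and 0.039 for correlations 0.3, 0.5 and 0.7.

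**3. Plausible information and correlation.** The documents give neither, so they were derived from patient-level simulation (12,000 trials per case). From 13.3: 363 subjects at 2:1, OS medians 3.9 and 6 months, and "subjects are assumed to be accrued at a rate of 19.2 per month with a drop-out rate of 10" per cent. Assumed: exponential times, equal EFS hazards in the two arms, progression independent of death, drop-out times with mean 6 months, and the EFS medians shown. The derived values then entered the normal model (4 million draws).

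| EFS median | EFS events at the two looks | Interim EFS information | Correlation, looks 1 and 2 | One-sided error, HR 0.65 | Two-sided total, HR 0.65 | Highest one-sided, HR 0.65-0.80 |
|---|---|---|---|---|---|---|
| 1 month | 235, 355 | 0.66 | 0.27, 0.23 | 0.0257 | 0.0455 | 0.0257 |
| 2 months | 206, 342 | 0.60 | 0.52, 0.47 | 0.0278 | 0.0431 | 0.0278 |
| 3 months | 181, 324 | 0.56 | 0.74, 0.71 | 0.0285 | 0.0376 | 0.0306 |

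Accrual of 363 over 17 months (21.4 per month) instead gives 0.0260, 0.0276 and 0.0284 at HR 0.65.

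**4. With EFS spending.** One-sided 0.025, EFS bounds at the two looks for information 0.66, 0.60 and 0.56:

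- O'Brien-Fleming type: 2.53 and 1.99; 2.67 and 1.98; 2.79 and 1.97.
- Pocock type: 2.08 and 2.24; 2.10 and 2.23; 2.13 and 2.22.

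The highest one-sided EFS error in the three cases falls to 0.018 and 0.019 respectively.

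**5. DMC wording.** No arithmetic applies. The limiting sentence in 13.10 follows a list of the formal interim outcomes. The same section names safety and benefit-risk analyses among the inputs to the futility decision. Section 5.5 allows termination for unacceptable risk, as an action involving sponsor, investigator or authorities and not as a DMC recommendation. Section 8.10.4 sends serious adverse events to the sponsor.

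**The case against.** Five objections deserve weight.

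- **The stated level is two-sided 0.05, and it holds.** The one-sided 0.025 in 13.10 is written for OS. This stands. A reader might double the one-sided 0.031 and conclude that EFS runs at about 0.06. That is wrong: the selection that raises the benefit tail lowers the harm tail, and no run gave a two-sided total above 0.049.
- **The excess is not general.** At low correlation with a weaker OS effect the error is below 0.025. This also stands.
- **The scenario is least favourable.** Equal EFS hazards with OS HR 0.65 require faster progression on quizartinib. For an EFS median of 3 months, the progression hazard ratio is (0.2310 − 0.1155)/(0.2310 − 0.1777) = 2.2; for 2 months and 1 month it is 1.4 and 1.1. Strong error control covers such cases, but they are not the expected ones.
- **The excess is about the size of the log-rank approximation error.** At 2:1 the test alone gives about 0.028 in this tail, and spending does not remove that. True, but it does not supply the missing bound.
- **Other documents may settle it.** A DMC charter, an Interim Analysis Plan and a separate SAP are cited but were not in the supplied text. Absence here does not show absence there.

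Two larger readings are tempting. Correlation 1 gives up to 0.041, and retesting EFS at the final look gives about 0.042. The documents provide for no retest, and the simulated correlations at HR 0.65 did not exceed about 0.74. On the DMC sentence, a reader might infer that a safety stop is barred. Section 5.5 keeps that route open, and the sentence may concern only the formal OS boundaries.

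**Conclusion.** The point holds in limited form. The order of testing alone does not guarantee one-sided 0.025 for EFS across two OS looks, and the supplied text gives no EFS bound at either. The excess in the benefit direction is at most about 0.006 (0.031 against 0.025) for correlations of 0.3 to 0.7, and it reverses in some settings. These figures rest on assumed EFS testing at z = 1.96 at the look where OS crosses, assumed correlations or EFS medians, and no EFS effect. The two-sided 0.05 in 13.5 and the synopsis is not shown to be broken, and OS error control and the 280 deaths are unaffected. This is worth considering, with medium confidence.

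The DMC sentence is a separate, minor conflict of wording. It does not show that the trial could not be stopped for risk.

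**What to change.** **EFS.** In 13.5 and the synopsis, prespecify a one-sided 0.025 alpha-spending function for EFS on its own information fraction, for example Lan-DeMets O'Brien-Fleming type. Test EFS only after OS is rejected, and at the EFS bound for that look. Align the SAP and Interim Analysis Plan, or cross-refer if they already set the bound.

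The text cost is a sentence in each place. The statistical cost is a stricter EFS bound if OS stops early: z about 2.5 to 2.8 (O'Brien-Fleming type) or about 2.1 (Pocock type) instead of 1.96. The Pocock type costs more at the final look (about 2.2 against 1.97 to 1.99). Either procedure is conservative here.

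**DMC.** Reconcile the limiting sentence in 13.10 with section 5.5 and with the safety and benefit-risk analyses that 13.10 itself lists, and align the DMC charter. No stopping rule is proposed.
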